3.0 Inclusion/Exclusion Criteria

Inclusion Criteria

For Soccer Cohort

- 1) being between 18 to 26 years of age
- 2) an active member of a soccer team (i.e., collegiate, intramural, club, professional)
- 3) at least 5 years of soccer heading experience.

For non-Athletic Control Cohort

- 1) Being between 18 to 26 years of age
- 2) Have never played organized sports
- 3) Have never been diagnosed with a concussion

Exclusionary criteria

For both Soccer and Non-Athletic Control cohorts

- 1) any head, neck, or face injury in the 1 year prior to the study (e.g., concussion, eye injury);
- 2) history of vestibular, ocular, or vision dysfunction (e.g., macular degeneration)
- 3) currently taking any medications affecting balance (e.g., antibiotics)
- 4) pregnancy
- 5) HIV
- 6) any neurological disorders (e.g., seizure disorders, closed head injuries with loss of consciousness greater than 15 minutes, CNS neoplasm, spinal cord injury/surgery, history of stroke)
- 7) hypertension, cardiac arrhythmia, or pulmonary disease
- 8) lower extremity injury that would prohibit normal walking
- 9) metal implants in the head
- 10) implantation of cochlear device, cardiac pacemaker, medical fusion device, intracardiac lines, or neurostimulator (e.g., DBS, epidural/subdural VNS)
- 11) history of severe injury to the bones, joints, or muscles in either arm

Session-specific exclusion criteria will include:

- 12) slept less than 4 hours before the 1st and 2nd test day (verified by the TMS screening questionnaire)
- 13) drank more than 3 alcoholic drinks or used recreational drugs 24 hours before the 1st and 2nd test day
- 14) drank more than 3 cups of coffee in an hour before test sessions
- 15) glasses are prohibited (contact lens are okay) for safety purpose for the heading intervention

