Peripheral diagnostic tools for brain injury have an immense clinical implication, however those methods are insufficient to truly gauge neuronal dysfunction after head hits. Electroencephalography (EEG) has produced promising results in patient with

[figure not shown]

Fig 3. PINCH protein was detectable in mesial temporal epilepsy patients' blood. Robust plasma expression of PINCH was observed in both medically controlled (no seizure) and refractory (transient seizure) epilepsy patients, while no PINCH in healthy controls.

[figure not shown]

Fig 4. Post-season plasma PINCH was notably higher than pre-season baseline. 10 out of 16 players showed increase in plasma PINCH at post-season. * Player 5 and 13 did not play for the season due to surgery. Control: a subject with no history of head trauma. LB, linebacker; OL, offense lineman; WR, wide receiver; DL, defense lineman; DB, defensive back; RB, running back; TE, tight end.

concussion, with reduced mean frequency of alpha, reduced power in the alpha and beta frequency bands, hypercoherence between frontal regions, and decreased gamma frequency.²⁵⁻²⁹ In addition to EEG, transcranial magnetic stimulation (TMS) has garnered significant attention in scientific society recently, due to its non-invasive method to measure neuronal excitability. However, to date, there is virtually no literature demonstrating the effects of minor head impacts on neuronal activity using EEG nor TMS.

Soccer Heading Modality

Soccer heading is a common skill performed by soccer athletes during practice and games. An average collegiate soccer players perform about 500 headers during a single season and over 3000 during the course of a career^{30, 31} Research has demonstrated the need for increased awareness of potential brain injury associated with heading the soccer ball with some suggesting that the cumulative effect of soccer head impacts over a career may lead to outcomes similar to sustaining multiple concussions.³² Various studies have been conducted to examine the effect of an acute bout of soccer heading, including [name] previous laboratory at Temple University, with most authors reporting no significant effect of heading on the brain function measures of neuropsychological or balance performance (Table 1). We have tested collegiate soccer players post heading ball speed up to 50 mph with no significant alterations in common

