2.0 Rationale and Specific Aims

Aim 1. Determine acute effects of subconcussive head impact on plasma PINCH and tau expression using controlled soccer heading model.

Hypothesis: Repetitive subconcussive head impacts will significantly increase plasma PINCH level at 24h-post heading, but plasma PINCH at 0h- and 2h-post heading will remain undetectable, while there will be a significant increase in serum tau level at immediately post-heading (0h and 2h) but normalize to baseline level at 24h-post heading.

After a concussion, a neural network is often disturbed due to axonal injury, observed via neuroimaging.^{34, 35} Also, an acute increase in plasma tau has been observed in concussed athletes.³⁶ However, a half-life of tau protein in the blood is known to be short (~3h),³⁷ thus at 24h-post heading tau level is expected to normalize to the pre-heading baseline level. Recent preliminary findings showed that neural disturbance was notable in football players at post-season compared with pre-season baseline, as well as rugby players after a single rugby game compared with pre-game level.^{38, 39} Although subconcussive impacts do not cause concussion-related symptoms,¹⁸ neuronal axons are evidently experiencing pathological stress.⁴⁰ Repetitive subconcussive impacts likely to cause tau injury, and because PINCH continues to be over-expressed in the brain as long as tau is

damaged,^{21, 22} a fraction of PINCH will be detectable in the peripheral blood stream via glymphatic system or disrupted blood-brain barrier.³⁷

Aim 2. Determine acute effects of subconcussive head impact on dynamic gaze-target synchronization in a controlled soccer heading model.

Hypothesis: Repetitive subconcussive head impacts will significantly decrease saccadic velocity and smooth pursuit velocity gain, and increase gaze position error variability.

Soccer heading model is a safe and reliable method to study mild head impacts, with average impact magnitude of 14 g.^{17, 33} To track a moving object, the brain must predict the trajectory of the moving target and maintain focus by concomitant adjustment of eye movement. We will employ the Eye-Sync system, which objectively measures important parameters, including smooth pursuit velocity gain, saccadic peak velocity, gaze position error variability.

Aim 3. Inspect subconcussive effects on changes in neuronal activity during resting default mode.

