When a subject who suffice inclusion criteria and free of exclusion criteria agree to participate in the study, he/she will be randomly assigned into one of three groups (heading, kicking-control, standing-control). A standardized and reliable soccer heading protocol will be used for the experiment. A triaxial accelerometer (Triax Technologies) embedded in a head-band pocket and positioned directly below the external occipital protuberance (inion) to monitor linear and rotational head accelerations. A JUGS soccer machine will be used to simulate a soccer throw-in with a standardized ball speed of 25mph across all 3 groups. The ball speed is similar to when soccer players make a long throw-in from the sideline to mid-field. Soccer players frequently perform this maneuver during practice and game. Subjects will stand approximately 40ft away from the machine to perform either the heading, kicking, or standing (Fig 5 & 6). [name] previous laboratory at Temple University has routinely employed the protocol and average linear head acceleration yielded from the header is 14.5g in which many of subconcussion studies in football and ice hockey have set a threshold of impact recording as 16g, indicating that impacts induced from our protocol are below the minimum magnitude recorded in other contact sports. Participants in the heading group perform 10 standing headers with 1 header per minute, whereas kicking control group performs 10 kicks. Standing control group will remain static while a soccer ball passes over the head. The subjects in the heading and kicking groups will be instructed to direct the ball back toward the JUGS soccer machine in the air, while the subjects in the standing group will remain static. The kicking and standing control groups will aid to

distinguish effects of subconcussive impact from exercise, bodily damage, and/or simply a daily variation of the outcome measures. The first phase of acute subconcussive effects will be measured at 0h-post heading, indicating immediate sensory perturbation and neuronal damage, followed by measurement of the second phase, 2h-post neural inflammatory response. Lastly, ocular-motor function coupled with neural activity at 24h-post heading will be measured to assess the third phase of subconcussive effects.

Procedure Outline

- 1. Email will be distributed**
- 2. Interested participants will contact PI (KK) to discuss Project**

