There is a risk of inducing symptoms such as headache, blurred vision, and disorientation during soccer heading testing, however ten soccer headers with mild head acceleration are commonly incorporated in soccer practice, and certainly soccer players utilize heading skill to direct a soccer ball for passing and scoring during practice and game. An average soccer player performs 500 headers over an entire season.^{30, 31} It is extremely unlikely to elicit concussion-like symptoms (headache, nausea, disorientation, blurred vision) from headings with mild head acceleration (Avg. 14.5g). The study protocol has been replicated in multiple laboratories, producing invaluable data to progress traumatic brain injury research. Moreover, our preliminary study in football players have shown that a player sustained 39 head hits with the total magnitude of 1,200g during a single practice, but with no change in symptoms.¹⁸ In order to minimize the risk of adverse events from soccer heading, we will only include soccer players who regularly play soccer and perform soccer headings.

Adverse Events Associated with Blood Draw

Complications of antecubital venous blood draws include bruising, local infection, phlebitis and injury to structures near the cubital vein. All of these complications are uncommon. To minimize these risks, [name]., (a certified phlebotomist) will perform the blood draws using single-use needles, tube holders and test tubes. The skin of the antecubital region will be cleaned with alcohol to further reduce the risks of infections. Following each blood draw the participant will remain seated while maintaining direct pressure against the site of the needle insertion. After each blood draw, the participant will be given a Band-aid to cover the puncture site. When the participant returns for each test session the certified phlebotomist will check the

puncture sites for any signs of complications (which would be referred for an additional medical examination).

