7.0 Study Withdrawal/Discontinuation

Data collection will require subjects to participate in 4 test sessions. Subjects may withdraw from the study at any time. A subject may also be withdrawn from the research without his/her consent if, for example, he/she 1) comes to the 1st and/or 2nd day with intoxication, 2) sustained injury prior to the 1st and 2nd day, 3) self-reported sleep deprivation for the 1st and/or 2nd day, 4) sustained a head injury prior to the 1st and 2nd day. If the subject completed for example entire 1st day procedure (3 test sessions) and unable to participate in the 2nd day (4th test session), the subject will be reimbursed hourly for the 1st day.

For non-athletic control cohort, we will evaluate and account for the soccer players' baseline, which may be influenced by a history of repetitive heading and sports participation. This group will participate in a single test session that lasts approximately in 1.5 hours. During the session, blood draw (4mL, about 1 teaspoon), measure eye movements using an ocular motor headset, and measure the brain activity using transcranial magnetic stimulation and electroencephalography. A subject may be terminated for the study participation if he/she 1) comes to the test session with intoxication, 2) sustained injury between screening and the day of test session, 3) self-reported sleep deprivation on the day of test session.

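### Off-study heading is neither restricted nor recorded before baseline or between the 2h and 24h visits, so the 24h result cannot be securely attributed to the ten study headers

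*Protocol*

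**What the plan says.** **Who is randomised.** Section 3.0 requires membership of a team: "an active member of a soccer team (i.e., collegiate, intramural, club, professional"). Section 6.0, under adverse events of soccer heading, says "we will only include soccer players who regularly play soccer and perform soccer headings". Regular heading is thus in effect an entry condition for all three groups.

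**Background exposure.** Section 1.0 states: "An average collegiate soccer players perform about 500 headers during a single season". Section 6.0 gives the same figure for an average player. Neither gives a daily or per-session rate.

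**Study exposure.** Section 5.0: "Participants in the heading group perform 10 standing headers with 1 header per minute". Kicking and standing controls receive no headers. Impact kinematics are measured only during the heading intervention.

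**Conduct rules.** The session-specific criteria in Section 3.0 cover sleep, coffee, glasses, and alcohol or drugs ("drank more than 3 alcoholic drinks or used recreational drugs 24 hours before the 1st and 2nd test day"). Section 7.0 allows withdrawal for intoxication, injury, sleep deprivation, or if the subject "sustained a head injury prior to the 1st and 2nd day". Neither list mentions practice, matches or heading.

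**Use of the data.** Section 8.0 makes the heading group's change from baseline at 0h, 2h and 24h the primary interest. The control groups help interpret it, and a second mixed model compares the groups. Aim 1 expects the heading bout to "significantly increase plasma PINCH level at 24h-post heading", with PINCH still undetectable at 0h and 2h.

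**The concern.** The trial studies ten mild, symptom-free head impacts in people whose ordinary sport supplies the same kind of impact. Subjects leave after the 2h visit and return the next day. If the plan is followed exactly, a subject in any group may train that evening, or come to baseline straight from practice, and nothing in the data would show it. The head-injury rule does not help, because Section 1.0 defines a subconcussive impact as one without concussion symptoms.

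Attribution is at stake. The kicking and standing groups are there to separate head impact from exercise, bodily impact and daily variation, which presumes that they have no head impacts. The 24h visit is the only one at which a PINCH rise is hypothesised, and it follows most of a day without supervision. The plan controls coffee in the hour before a session and alcohol in the 24 hours before each test day, but not its own exposure over the same period.

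**Working it through.** **Inputs from Section 8.0:** difference 0.55, SD 0.6, two-sided 5% (1.96), power 0.80 (0.8416), 20 per group. **Assumptions not in the documents:** a share f of subjects heads the ball off study, with f = 0.10, 0.25 or 0.50, and the effect of doing so equals that of the study bout (0.55).

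**Step 1. Reproduce the plan's figure.** n = 2(1.96 + 0.8416)² × 0.6² / 0.55² = 18.68 per group, as stated. The standardised difference is 0.55 / 0.6 = 0.917. With 20 per group, a two-sample t-test has power 0.81 (the normal approximation gives 0.826).

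**Step 2. Between groups at 24h, extra heading equal and additive in all groups.** The difference stays at 0.55. A mixture of exposed and unexposed subjects adds f(1−f) × 0.55² to the variance, so SD = √(0.36 + f(1−f) × 0.3025).

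| f | SD | Standardised difference | Power, n = 20 |
|---|---|---|---|
| 0 | 0.600 | 0.917 | 0.81 |
| 0.10 | 0.622 | 0.88 | 0.78 |
| 0.25 | 0.646 | 0.85 | 0.75 |
| 0.50 | 0.660 | 0.83 | 0.73 |

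**Step 3. Between groups at 24h, only controls gain** (the effect has a ceiling, or controls head the ball and the heading group does not). The difference becomes 0.55(1−f), with SD kept at 0.6.

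| f | Difference | Standardised difference | Power, n = 20 |
|---|---|---|---|
| 0.10 | 0.495 | 0.83 | 0.72 |
| 0.25 | 0.413 | 0.69 | 0.56 |
| 0.50 | 0.275 | 0.46 | 0.29 |

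**Step 4. Within the heading group, the primary contrast.** If a share f heads again after the 2h visit and effects add, the expected 24h change is 0.55(1+f): 0.605 at f = 0.10 and 0.825 at f = 0.50. If a share f headed before baseline, and that effect is present at baseline but gone by the later visit, the expected change is 0.55(1−f): 0.495 and 0.275. The bias can go either way.

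**Step 5. Which visits.** Baseline, 0h and 2h fall within a first day of 4.5 hours. Heading after the 2h visit touches only the 24h result. The 0h and 2h results are affected only through a disturbed baseline. Tau is the plausible case, since Section 2.0 expects an early rise and cites a half-life of about 3 hours.

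**The case against.** A reader might infer that the 24h between-group contrast is necessarily diluted. The documents do not support that. Allocation is random, so off-study heading is expected equally in all three groups. If effects add, the between-group difference is unbiased and only noisier (Step 2). Dilution needs a ceiling effect or more heading among controls, and the protocol gives evidence for neither.

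Three further objections have force:

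- **Size.** The season figure cannot be turned into a rate for the test window. Recruitment also admits intramural and club players, who may head the ball less than collegiate players. The 0.55 and 0.6 are general planning values, not a 24h PINCH estimate.
- **Baseline.** A tau rise after heading is a hypothesis in Aim 1, so it cannot be stated as fact that practice raises baseline tau. The 20 non-athletic controls are recruited to check whether players' baselines are comparable. They may show a raised group baseline. But they are tested once, so they cannot correct one player's recent practice or reveal heading between 2h and 24h.
- **Completeness.** The consent form and the health-history and TMS questionnaires are not shown, and an instruction or question could be there.

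These limit what can be said about direction and size. They do not remove the gap: no rule shown in the protocol restricts the exposure or records it outside the intervention.

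**Conclusion.** The point holds as one of attribution, not as a demonstrated dilution. The randomised subjects are regular headers of the ball, and off-study heading is neither restricted nor counted before baseline or between 2h and 24h. The primary within-heading-group change at 24h may be inflated or masked. The between-group contrast is at best noisier (power 0.81 to 0.78–0.73) and at worst diluted (0.72–0.29), for assumed shares of 10% to 50%. Both ranges rest on an off-study effect equal to the study bout and on the plan's own 0.55 and 0.6. They show what could happen and do not estimate what will. Without a record of exposure, the analysis cannot tell these cases apart. The matter should be corrected; it does not invalidate the design.

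**What to change.** 1. Add to the session-specific criteria in Section 3.0, for all three groups: no heading and no contact practice from a stated window before baseline until the 24h visit is complete. The 24 hours already used for alcohol and drugs is one possible window.
2. Schedule test days away from team sessions.
3. On both test days, ask for and record the number of off-study headers: in the window before baseline on day 1, and since the 2h visit on day 2.
4. Keep all randomised subjects in the main analysis whatever they report. Use the recorded count only in a supportive sensitivity analysis, because excluding subjects by heading after randomisation can itself bias the comparison.

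The sample size does not change. The cost is one instruction, one question per test day, and slightly harder scheduling in season.

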4.0 Enrollment/Randomization

Potential participants will be recruited via listserv email to undergraduate students in the School of Public Health-Bloomington, and interested participants will contact (phone or email) and meet with the investigator to discuss the project and ask questions. The informed consent and Concussion History & Health History Questionnaire will be given to the potential candidates. Participants who meet the inclusion criteria and are free of exclusionary factors will advance to the testing procedures.

We will use simple randomization method for group assignments. Upon inclusion of the participants, based on dice roll they will be randomly assigned into one of three groups: Heading group (number of dice 1 or 2), kicking group (number of dice 3 or 4), or standing group (number of dice 5 or 6). After assigned to groups, based on flipping a two-sided coin, participants will be further assigned into either TMS (head) or EEG (tail) experiments.

[name] (PI) will only know subjects' group assignment and ensure blinded experiment and data processing. [name] will randomly assign participants into three groups and perform soccer heading/kicking/standing protocol, and draw blood. Ocular-motor testing and data processing will be performed by [name] and blood biomarker experiments will be performed by [name]. The EEG experiment will be conducted by [name] and analyzed by [name]. The TMS experiment will be performed by [name] and analyzed by [name]. As noted, statistical analyses of all the data will be performed by [name]. These process will ensure single blind method.

5.0 Study Procedures

Research Design

We will use a repeated measures design. The independent variable will be time (pre-test, 0h post-test, 2h post-test, 24h post-test). Control groups (kicking and standing) will be used to analyze any effects from bodily damage, exercise, and normal changes in dependent variables over time. The dependent variables assessed over time will include symptom scores, ocular-motor function, blood biomarker concentration, brain waves, and cortical excitability. Impact kinematics will also be assessed during soccer heading.

The study consists of 4 data collection time points in 2-day period. The 1st collection - pre-heading baseline-, followed by soccer heading intervention. The 2nd collection, 0h-post-heading time point (immediately after headings). The 3rd collection, 2h-post-heading time point (2h after headings). The 4th collection, 24h-post-heading time point (2nd day). This study design will enable to test outcome measures over 3 acute phases (Figure 5). The 1st day will last 4.5 hours and 2nd day will last 1.5 hours. Since we propose to include a total of 60 subjects in the study, we estimate data collection and primary analysis of 60 subjects will last approximately 15 months.

In order to address the potential residual effects of previous soccer-related injury or head trauma, we will recruit additional 20 age- and gender-matched healthy-non-athletic controls, against subjects in the soccer heading group to validate whether baseline values of each parameter are comparable to a healthy non-athletic cohort. However, regardless of whether there will be a difference in baseline between soccer players and healthy-controls, the purpose of the current study is to determine acute subconcussive head impact effects in the athletic population. Thus, the changes between soccer players and healthy controls will not terminate the study.

Soccer Heading Protocol

When a subject who suffice inclusion criteria and free of exclusion criteria agree to participate in the study, he/she will be randomly assigned into one of three groups (heading, kicking-control, standing-control). A standardized and reliable soccer heading protocol will be used for the experiment. A triaxial accelerometer (Triax Technologies) embedded in a head-band pocket and positioned directly below the external occipital protuberance (inion) to monitor linear and rotational head accelerations. A JUGS soccer machine will be used to simulate a soccer throw-in with a standardized ball speed of 25mph across all 3 groups. The ball speed is similar to when soccer players make a long throw-in from the sideline to mid-field. Soccer players frequently perform this maneuver during practice and game. Subjects will stand approximately 40ft away from the machine to perform either the heading, kicking, or standing (Fig 5 & 6). [name] previous laboratory at Temple University has routinely employed the protocol and average linear head acceleration yielded from the header is 14.5g in which many of subconcussion studies in football and ice hockey have set a threshold of impact recording as 16g, indicating that impacts induced from our protocol are below the minimum magnitude recorded in other contact sports. Participants in the heading group perform 10 standing headers with 1 header per minute, whereas kicking control group performs 10 kicks. Standing control group will remain static while a soccer ball passes over the head. The subjects in the heading and kicking groups will be instructed to direct the ball back toward the JUGS soccer machine in the air, while the subjects in the standing group will remain static. The kicking and standing control groups will aid to

distinguish effects of subconcussive impact from exercise, bodily damage, and/or simply a daily variation of the outcome measures. The first phase of acute subconcussive effects will be measured at 0h-post heading, indicating immediate sensory perturbation and neuronal damage, followed by measurement of the second phase, 2h-post neural inflammatory response. Lastly, ocular-motor function coupled with neural activity at 24h-post heading will be measured to assess the third phase of subconcussive effects.

Procedure Outline

- 1. Email will be distributed**
- 2. Interested participants will contact PI (KK) to discuss Project**
